6.4. Visit Windows

Data analyzed by-visit-analysis (including efficacy, laboratory data, visit sign, ECG) will be summarized by the study scheduled visits described [Appendix 11.2](#), “Schedule of Event”. The analysis visit windows will be exhaustive so that all available values obtained from unscheduled visits and early termination (ET) visit have the potential to be summarized. No analysis visit windows will be applied for the study scheduled visits. The visit windows are constructed using ranges applied to the number of days in study (study days) when the measure is collected.

The following analysis visit windows will be used to map the unscheduled visits and ET visits, based on the study day:

Visit	Target Day (TD)	Analysis Time Window Based on Study Day
Visit 1 (Screening)	-30 to -1	-29 to -2
Visit 2 (Baseline)	1	1
Visit 3	5	[4, 6]
Visit 4	10	[8, 12]
Visit 5	30	[27, 33]

Visit 6 (End of Study)	75	[70, 80]
------------------------	----	----------

Notes:

1. Additional visits will be created as needed depending on the aPTT results per cohort
2. End of Study visit will be mapped according to its actual day

In general, the following order will be used to select the record for analysis at give visit:

1. Scheduled visit
2. Early termination (ET) or end of study (EOS), whichever comes first if scheduled visit is not available
3. Unscheduled visit if both scheduled visit and ET/EOT/EOS are not available

For multiple measurements of the same test in the same window, the following rules will be used to select the analysis value:

1. If multiple valid values of a variable within an analysis visit window, the closest from the target study day will be selected.
2. If the difference is a tie, the value after the target study day will be used.
3. If multiple available values of a variable exist within a same day, then the first value of the day will be selected

7. INTERIM ANALYSIS

An informal IA will be conducted by the sponsor when there are approximately 50 participants per arm who have evaluable primary endpoints (i.e. adjudicated, evaluable venography or confirmed VTE through day 12).

The IA will only be used for administrative purpose and will not be used to make any decisions regarding the conduct of this study.

The IA may include safety, efficacy and demographic and other baseline characteristics variables.

8. STUDY COMMITTEES

8.1. Independent Data Monitoring Committee

The IDMC (also known as a Data Monitoring Safety Board) is an independent, multidisciplinary group consisting of clinicians and statistician(s) that, collectively, have experience in areas relevant to this clinical study and in the conduct and monitoring of randomized clinical studies.

The IDMC is independent from Regeneron and the study investigators and will perform regular safety data assessment of study participants and provide recommendations to Regeneron regarding the safety and the welfare of the participants exposed to REGN9933.

Detailed information regarding the DMC procedures are provided in a separate DMC charter.

8.2. Steering Committee

The Steering Committee is composed of independent experts, selected by Regeneron. The Steering Committee will provide advice on all scientific matters (including protocol development and publication of results) related to the study.

Details are provided in a separate Steering Committee charter.

8.3. Adjudication Committee

The AC is comprised of independent experts selected by Regeneron. The AC will review and determine interpretation and/or classification of the following events and tests in a blinded manner: all imaging procedures used for determination of VTE, including mandatory venography and testing for suspected DVT or PE; all deaths; all suspected bleeding events.

Details are explained in a separate Adjudication Committee charter.

9. SOFTWARE

All analyses will be done using SAS Version 9.4 or higher, and R version 3.5.0 or higher.

11. APPENDIX

11.1. Summary of Statistical Analyses

Table 1: Efficacy/PD Analyses

Endpoint	Analysis Populations	Primary Statistical Method/Analysis	Sensitivity Analysis	Subgroup Analysis	Other Analyses
Primary Endpoint					
Proportions of participants with adjudicated, confirmed VTE through day 12	mITT	Bayesian logistic regression	Stratified CMH analysis	Yes	No
Secondary/PD Endpoints					
Secondary efficacy endpoints	mITT	Bayesian logistic regression	Stratified CMH analysis	Yes	No
aPTT, PT	PDAS	Descriptive Statistics	No	No	No
FXI:C, TGA	PDAS	Descriptive Statistics	No	No	No

Table 2: Safety Analyses

Endpoint	Analysis Populations	Statistical Method	Supportive Analysis	Subgroup Analysis	Other Analyses
Adverse Events	SAF	Descriptive Statistics	No	No	No
Laboratory Measures	SAF	Descriptive Statistics	No	No	No
Vital Signs	SAF	Descriptive Statistics	No	No	No
ECG	SAF	Descriptive Statistics	No	No	No

11.2. Schedule of Time and Events

Table 3: Schedule of Events

Study Procedure	Screening	On-treatment			Follow-up	
	Visit 1	Baseline Visit 2	Visit ^{1,2} 3	Visit ¹ 4	Visit 5	End of Study/ Visit 6
Day	-30 to -1	1	5	10	30	75
Window (day)			±1	±2	±3	±5
Screening/Baseline:						
Inclusion/Exclusion	X					
Informed consent	X					
Informed consent for pharmacogenomics research (optional)	X					
Informed consent for future biomedical research (optional)	X					
Medical History	X					
Demographics	X					
FSH ³	X					
GFR (MDRD)	X					
Urine drug screen	X					
Randomization		X ⁴				
Treatment:						
TKA		X				
Administer REGN9933		X ⁵				
Administer enoxaparin			X ⁶			
Administer apixaban			X ⁶			
Participant diary (for self-administration of apixaban/enoxaparin)			X			
Efficacy:						
Venography of the operated leg				X		
Assessment for symptomatic VTE ⁷		X	X	X	X	X
Safety:						
Height	X					
Weight	X					
Vital Signs	X	X	X	X	X	X
Physical examination	X	X				X
Electrocardiogram	X					
Assessment for surgical site bleeding		X	X	X		
Assessment for bleeding events		X	X	X	X	X
Adverse events	X	X	X	X	X	X
Concomitant medications and treatment	X	X	X	X	X	X
Laboratory Testing						
Hematology	X	X ⁸		X		X
Blood chemistry	X	X ⁸		X		X

Study Procedure	Screening	On-treatment			Follow-up	
	Visit 1	Baseline Visit 2	Visit ^{1,2} 3	Visit ¹ 4	Visit 5	End of Study/ Visit 6
Coagulation panel	X	X ⁸		X		X
Urinalysis	X					X
Pharmacokinetics and Immunogenicity Sampling						
Drug concentration sample (REGN9933)		X ⁸	X	X	X	X
ADA (REGN9933)		X ⁹				X
Plasma for total FXI concentration		X ⁸	X	X	X	X
Biomarkers						
Plasma for aPTT, PT (central lab)		X ⁸	X	X	X	X
Plasma for FXI activity (FXI:C) and TGA		X ⁸	X	X	X	X
Serum for exploratory research		X ⁸	X		X	X
Plasma for exploratory research		X ⁸	X		X	X
Optional Pharmacogenomics samples						
Whole blood sample for RNA isolation (optional) ¹⁰		X				X
Whole blood sample for DNA isolation (optional) ¹⁰		X ¹¹				

ADA: anti-drug antibody; aPTT: activated partial thrombin time; GFR: glomerular filtration rate; FSH: follicle-stimulating hormone; FXI: Factor XI; FXI:C: Factor XI functional activity; MDRD: Modification of Diet in Renal Disease; PT: prothrombin time; TGA: thrombin generation assay; TKA: total knee arthroplasty; VTE: venous thromboembolism

11.2.1. Footnotes for the Schedule of Events

1. Assessments for this visit may be performed in the hospital if the participant has not yet been discharged.
2. If the participant is discharged prior to this visit, then information may be collected by telephone call, and assessments requiring blood draw may be omitted.
3. To be performed in women 55 years of age or younger.
4. Randomization will occur after completion of surgery on day 1.
5. Dosing will occur 12 to 24 hours after the end of surgery, and at least 12 hours after removal of the needle/catheter used for spinal/epidural anesthesia.
6. First dose will be given 12 to 24 hours after the end of surgery.
7. May include confirmatory studies for DVT of the leg or PE, as described in protocol Section 9.2.2.2. Confirmatory studies for suspected DVT of the leg or PE may be required more than once, per the discretion of the investigator.
8. Refer to Table 4 for detailed information on Visit 2 samples.

9. Samples for ADA must be collected prior to dose administration on the same day that study drug is administrated. Refer to Table 4.
10. The genomics sub-study informed consent form (ICF; for RNA and DNA analysis) must be signed prior to performing this sample collection.
11. Samples for DNA extraction should be collected at the baseline visit (predose) but may also be collected at any later study visit.

Table 4: Schedule of Events: Visit 2 Blood Collection

Baseline Visit 2 (Day 1)			
Study Procedure	Pre-operatively	Post-operatively	
		Pre-dosing Up to 1 hour prior to dosing	Post-dosing REGN9933 only: as close as possible to 1- hour post-dose
Laboratory Testing			
Hematology	X ¹		
Blood chemistry	X ¹		
Coagulation panel	X ¹		
Urinalysis			
Pharmacokinetics and Immunogenicity Sampling			
Drug concentration sample (REGN9933)		X ²	X ²
ADA (REGN9933)		X ²	
Plasma for total FXI concentration	X ¹	X ³	X ²
Biomarkers			
Plasma for aPTT, PT (central lab)	X ¹	X ³	X ²
Plasma for FXI activity (FXI:C) and TGA	X ¹	X ³	X ²
Serum for exploratory research	X ¹	X ³	
Plasma for exploratory research	X ¹	X ³	

ADA: anti-drug antibody; aPTT: activated partial thrombin time; FXI: Factor XI; FXI:C: Factor XI functional activity; PT: prothrombin time; TGA: thrombin generation assay

11.2.2. Footnotes for Schedule of Events: Visit 2 Blood Collection

1. Samples may be collected up to 24 hours prior to surgery. Samples to be collected in all 3 treatment groups.
2. Samples to be collected in REGN9933 group only.
3. Samples to be collected in all 3 treatment groups.

11.3. Criteria for Potentially Clinically Significant Values (PCSV)

Parameter	PCSV Criteria	Comments and References
Clinical Chemistry		
ALT*	
>3 ULN and baseline \leq1 ULN*
 
>6 ULN and baseline \leq3 ULN
	
Enzyme activity must be expressed in ULN, not in IU/L.
 
U. S. Food and Drug Administration. Center for Drug Evaluation and Research. (2009). Drug-Induced Liver Injury: Premarketing Clinical Evaluation
 
Each category is calculated independently.

AST*	
>3 ULN and baseline \leq1 ULN*
 
>6 ULN and baseline \leq3 ULN
	
Enzyme activity must be expressed in ULN, not in IU/L.
 
U. S. Food and Drug Administration. Center for Drug Evaluation and Research. (2009). Drug-Induced Liver Injury: Premarketing Clinical Evaluation
 
Each category is calculated independently.
 
* At least one level is required, multiple levels are optional for phase 2/3 studies. If it is desirable to get the distribution across the different PCSV levels, additional shift table on \leq3, >3 to \leq5, > 5 to \leq10, >10 to \leq20, and > 20 category for baseline vs. post baseline may be provided

Alkaline Phosphatase	
>2.5 ULN and baseline \leq1.5 ULN
	
Enzyme activity must be expressed in ULN, not in IU/L.
 
U. S. Food and Drug Administration. Center for Drug Evaluation and Research. (2009). Drug-Induced Liver Injury: Premarketing Clinical Evaluation

Total Bilirubin*	
>2 ULN and baseline \leq1.5 ULN
	
Must be expressed in ULN, not in μmol/L or mg/L. Categories are cumulative.
 
U. S. Food and Drug Administration. Center for Drug Evaluation and Research. (2009). Drug-Induced Liver Injury: Premarketing Clinical Evaluation
 
* At least one level is required, multiple levels are optional for phase 2/3 studies. If it is desirable to get the distribution of significant level, additional shift table on \leq1.5, >1.5 to \leq2.0 and > 2.0 category for baseline vs. post baseline may be provided

ALT and Total Bilirubin	
ALT>3 ULN and TBILI>2 ULN, and baseline ALT \leq1 ULN or TBILI \leq1.5ULN
	
U. S. Food and Drug Administration. Center for Drug Evaluation and Research. (2009). Drug-Induced Liver Injury: Premarketing Clinical Evaluation

Parameter	PCSV Criteria	Comments and References
Creatinine	$\geq 150 \mu\text{mol/L}$ (Adults) and baseline $< 100 \mu\text{mol/L}$ $\geq 30\%$ change from baseline $\geq 100\%$ change from baseline	Benichou C., 1994. 3 independent criteria
Blood Urea Nitrogen	$\geq 30 \text{ mmol/L}$ and baseline $< 17 \text{ mmol/L}$	One independent criteria
Sodium Hyponatremia Hypernatremia	$\leq 125 \text{ mmol/L}$ and baseline $> 129 \text{ mmol/L}$ $\geq 160 \text{ mmol/L}$ and baseline $< 155 \text{ mmol/L}$	Two independent criteria
Potassium Hypokalemia Hyperkalemia	$< 3 \text{ mmol/L}$ and baseline $\geq 3 \text{ mmol/L}$ $\geq 5.5 \text{ mmol/L}$ and baseline $< 4.9 \text{ mmol/L}$	FDA Feb 2005. Two independent criteria
Glucose Hypoglycaemia Hyperglycaemia	$\leq 3.9 \text{ mmol/L}$ and $< \text{LLN}$ and baseline $> 5.9 \text{ mmol/L}$ $\geq 11.1 \text{ mmol/L}$	ADA Jan 2008.
Albumin	$\leq 32 \text{ g/L}$ and baseline $> 35 \text{ g/L}$	
Hematology		
WBC	$< 2.0 \text{ Giga/L}$ and baseline $\geq 4.0 \text{ Giga/L}$ $\geq 16.0 \text{ Giga/L}$ and baseline $< 10 \text{ Giga/L}$	Increase in WBC: not relevant. *The default criteria. Summary by race (black and Non-black) are optional. To be interpreted only if no differential count available.
Neutrophils	$< 1.0 \text{ Giga/L}$ and baseline $\geq 2 \text{ Giga/L}$	International Consensus meeting on drug-induced blood cytopenias, 1991.
Eosinophils	$> 1 \text{ Giga/L}$ and baseline $\leq 0.4 \text{ Giga/L}$	Harrison- Principles of internal Medicine 17 th Ed., 2008.
Hemoglobin	$\leq 10 \text{ g/L}$ and baseline $> 12 \text{ g/L}$ *Decrease from Baseline $\geq 30\%$	Two criteria are independent. Criteria based upon decrease from baseline are more relevant than based on absolute value. Other categories for decrease from baseline can be used ($\geq 30 \text{ g/L}$, $\geq 40 \text{ g/L}$, $\geq 50 \text{ g/L}$). *based on expected post-operative changes

Parameter	PCSV Criteria	Comments and References
Hematocrit	≤ 0.32 v/v and baseline >0.38 v/v *Decrease from Baseline $\geq 30\%$	The first criteria is the follow up value. *based on expected post-operative changes
Platelets	<50 Giga/L and baseline ≥ 100 Giga/L ≥ 700 Giga/L and baseline <400 Giga/L	International Consensus meeting on drug-induced blood cytopenias, 1991. Two independent criteria
Vital signs		
HR	≤ 50 bpm ≥ 130 bpm	To be applied for all positions except STANDING.
SBP	≤ 95 mmHg and decrease from baseline ≥ 20 mmHg ≥ 165 mmHg and increase from baseline ≥ 20 mmHg	To be applied for all positions except STANDING.
DBP	≤ 45 mmHg and decrease from baseline ≥ 10 mmHg ≥ 105 mmHg and increase from baseline ≥ 10 mmHg	To be applied for all positions except STANDING.
ECG		
HR	≤ 45 bpm ≥ 130 bpm	Two independent criteria and evaluate follow up values.
PR	≥ 220 ms	
QRS	≥ 120 ms	
QTc Prolonged**	Prolonged: >450 ms for male or >470 ms for female	QT correction formula to be applied is the Fridericia. *The default criteria. By gender (male and female) are optional. **QTc prolonged and $\Delta QTc > 60$ ms are the PCSV to be identified in individual subjects/patients listings.

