7.2.1. Inclusion Criteria

A participant must meet the following criteria to be eligible for inclusion in the study:

1. Is a male or female ≥ 50 years of age at the screening visit, undergoing elective unilateral TKA.
2. Has a body weight ≤ 130 kg at screening visit.
3. Is judged by the investigator to be in good health based on medical history, physical examination, vital sign measurements, and ECG's performed at screening and/or prior to administration of initial dose of study drug.
4. Is in good health based on laboratory safety testing obtained during the screening period:
 - a. Platelet count > 150 K
 - b. Normal PT, international normalized ration (INR), and aPTT during screening
 - c. Hemoglobin > 10 g/dL
 - d. Alanine aminotransferase (ALT) or aspartate aminotransferase (AST) $< 3X$ upper level of normal (ULN), or total bilirubin $< 2X$ ULN

Note: Participants with suspected or confirmed Gilbert's disease can be enrolled in the study

5. Willing and able to comply with clinic visits and study-related procedures including venography.
6. Provide informed consent signed by study participant.

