4.5.2. Bleeding Events

The ISTH criteria will be used for both major bleeding events and CRNM events as described below. Minimal bleeding will be captured separately as an exploratory endpoint.

Major bleeding, CRNM bleeding and minimal bleeding through time of venography (or day 12, whichever is earlier) and through the end of study will be summarized by each treatment group.

Major Bleeding (ISTH):

- Fatal bleeding and/or
- Bleeding that is symptomatic and occurs in a critical area or organ, such as intracranial, intraspinal, intraocular, retroperitoneal, pericardial, in a non-operated joint, or intramuscular with compartment syndrome, assessed in consultation with the surgeon, and/or
- Overt extra surgical site bleeding causing a fall in hemoglobin level of 20 g/L (1.24 mmol/L) or more, or leading to transfusion of two or more units of whole blood or packed red cells, with temporal association within 24 to 48 hours to the bleeding, and/or
- Surgical site bleeding that requires a second intervention (open, arthroscopic, endovascular) or a hemarthrosis of sufficient size as to interfere with rehabilitation by delay

in mobilization or delayed wound healing, resulting in prolonged hospitalization or a deep wound infection, and/or

- Surgical site bleeding that is unexpected and prolonged and/or is sufficiently large to cause hemodynamic instability, as assessed by the surgeon. There should be an associated fall in hemoglobin level of at least 20 g/L (1.24 mmol/L), or transfusion indicated by the bleeding, of at least two units of whole blood or red cells, with temporal association within 24 hours to the bleeding.

Clinically Relevant Non-Major Bleeding (ISTH):

- Any sign or symptom of hemorrhage (e.g., more bleeding than would be expected for a clinical circumstance, including bleeding found by imaging alone) that does not fit the criteria for the ISTH definition of major bleeding but does meet at least one of the following criteria:
 - requiring medical intervention by a healthcare professional
 - leading to hospitalization or increased level of care
 - prompting a face to face (i.e., not just a telephone or electronic communication) evaluation

Minimal Bleeding:

Any overt bleeding event that does not meet the criteria for either major or CRNM bleeding will be categorized as a minor bleeding event. Minimal bleeding will be captured separately as an exploratory endpoint.

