5.8.3. Analysis of Clinical Laboratory Measurements

Laboratory measurements include clinical chemistry, hematology and urinalysis results, and will be converted to standard international units and US conventional units. Summaries of laboratory variables will include:

- Descriptive statistics of laboratory result and change from baseline by visit
- The number (n) and percentage (%) of participants with treatment-emergent PCSVs during study
- Shift tables based on baseline normal/abnormal may be used to present the results for parameters of interest

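### The absolute hemoglobin PCSV in SAP 11.3 is printed in g/L with numbers that fit g/dL; applied as printed it flags no one whom the 30% decrease rule does not already flag.

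*SAP*

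**What the plan says.** The hemoglobin row of SAP 11.3 has two criteria, which its comment cell describes as independent, so either one flags a participant. The absolute criterion is "\leq 10 \text{ g/L}$ and baseline $> 12 \text{ g/L": follow-up at most 10 g/L, baseline above 12 g/L. The relative criterion is "Decrease from Baseline $\geq 30" percent. The comment cell ranks decrease-based criteria above the absolute one and adds "Other categories for decrease from baseline can be used", listing falls of 30, 40 and 50 g/L.

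Other places that bear on it:

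- Protocol 7.2.1, inclusion criterion 4c: "Hemoglobin > 10 g/dL".
- SAP 4.5.2, major bleeding: "a fall in hemoglobin level of 20 g/L (1.24 mmol/L) or more".
- SAP 11.3, hematocrit row: at most "0.32 v/v and baseline >0.38 v/v", plus its own 30% rule.
- SAP 5.8.3: laboratory results "will be converted to standard international units and US conventional units", and the tables give the number and "percentage (%) of participants with treatment-emergent PCSVs during study".

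**The concern.** The numbers 10 and 12 are ordinary hemoglobin values in g/dL, not in g/L. SAP 5.8.3 produces results in both unit systems, so a programmer who follows the table literally has a g/L variable to which the printed cut can be applied. One of the two stated hemoglobin criteria would then do nothing, without any error message. In a trial of an anticoagulant, with bleeding as a secondary endpoint, the by-arm count of low hemoglobin values should work as specified. If the intended cut was 100 g/L from a baseline above 120 g/L, the literal version undercounts for part of the baseline range.

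**Working it through.** The check needs only unit conversion (1 g/dL = 10 g/L) and a comparison of the two criteria.

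**1. Scale.** The entry floor is 10 g/dL = 100 g/L. The printed follow-up cut is 10 g/L, and 100 / 10 = 10, so the cut is a tenth of the floor. This comparison alone gives the factor of ten. The optional falls of 30, 40 and 50 g/L in the same row, and the 20 g/L fall in the bleeding definition, are changes rather than levels. They show that the scale is wrong because each exceeds the whole printed baseline of 12 g/L.

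**2. What the printed criterion adds in g/L.** Let B be baseline and v follow-up. The 30% rule flags v ≤ 0.7B. The absolute criterion adds a flag only if v ≤ 10, B > 12 and v > 0.7B. That requires 0.7B < 10, so B < 10 / 0.7 = 14.29 g/L.

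- At the entry floor, a value of 10 g/L is a fall of (100 − 10) / 100 = 90%, which the 30% rule already flags.
- A scan in 0.1 g/L steps over baselines above 100 and up to 200 g/L found no additional flag.
- The condition B > 12 g/L excludes no eligible participant.

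**3. What is lost if 100 and 120 g/L were meant.** The same algebra gives an upper bound of 100 / 0.7 = 142.9 g/L. For baselines above 120 and below 142.9 g/L, the absolute criterion would flag values above 0.7B and up to 100 g/L that the 30% rule misses.

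| Baseline (g/L) | 0.7 × baseline | Follow-up range lost (g/L) | Fall needed to reach 100 g/L |
|---|---|---|---|
| 121 | 84.7 | above 84.7 to 100 | 17.4% |
| 130 | 91.0 | above 91.0 to 100 | 23.1% |
| 140 | 98.0 | above 98.0 to 100 | 28.6% |
| 142.9 | 100.0 | none | 30.0% |

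For example, 125 to 98 g/L (a 21.6% fall) and 130 to 98 g/L (24.6%) would be flagged by the absolute criterion only.

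**4. How much the hematocrit row recovers.** The documents give no hemoglobin-to-hematocrit ratio. As an assumption, take a ratio r of 320 to 360 g/L, the same at baseline and follow-up. The hematocrit cuts then correspond to hemoglobin values of 0.32r and 0.38r:

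| r (g/L) | 0.32r (follow-up cut) | 0.38r (baseline cut) |
|---|---|---|
| 320 | 102.4 | 121.6 |
| 340 | 108.8 | 129.2 |
| 360 | 115.2 | 136.8 |

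The follow-up cut lies above 100 g/L throughout, so only the baseline condition limits the overlap. Cases missed by both rows are then confined to baselines from just above 120 g/L up to 121.6, 129.2 or 136.8 g/L. This fails for r below 100 / 0.32 = 312.5 g/L, where the hematocrit follow-up cut drops under 100 g/L.

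**The case against.** The text was read from PDF by software, and a reader that dropped the letter d would turn g/dL into g/L. That cannot be excluded without the source page. It would have to happen twice in the same cell, while the g/L figures in the adjacent cell came through at a sensible scale, so it is unlikely; a look at the page settles it.

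The proof from the entry floor does not cover every baseline. SAP 6.1 takes the latest valid value before study drug, so an unscheduled post-operative value below 100 g/L could serve. The only hematology sample scheduled at Visit 2 is pre-operative, however, and a baseline under 14.29 g/L is not plausible in any case. Where baseline is missing, the 30% rule cannot be computed. SAP 6.3 might then leave the absolute cut as the only test, but at 10 g/L it would flag essentially no one.

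The strongest point is that an undercount is conditional. It requires both that 100 and 120 g/L were intended and that the program applies the printed unit. If 10 and 12 are applied to g/dL values, the criterion works. The slip is also conspicuous beside falls of 30 to 50 g/L, so a programmer may well notice it. This stands, and it limits the finding to a wrong printed unit with a possible consequence for the count.

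Materiality is low. Laboratory PCSVs are descriptive, the SAP itself prefers decrease-based criteria, and the 30% rule carries a note that it allows for expected post-operative change. All of that is accepted.

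**Conclusion.** The concern holds, as a minor one. The hemoglobin criterion is wrong as written: its unit contradicts the entry criterion by a factor of ten and is off scale against the falls in its own row and in the bleeding definition. Followed literally in g/L, it contributes nothing beyond the 30% rule for any baseline of 14.29 g/L or more, which means for every participant.

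Whether any reported count is affected depends on the unit in the program, which the documents do not state. On the reading of 100 and 120 g/L, the loss in the hemoglobin row is limited to falls of under 30% ending at or below 100 g/L, from baselines above 120 and below 142.9 g/L. The hematocrit row recovers part of it, by an amount that rests on the assumed ratio. Hemoglobin change from baseline by visit, adjudicated ISTH bleeding, the efficacy analyses and the sample size are unaffected.

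**What to change.** In the hemoglobin row of SAP 11.3, state the absolute thresholds in one unit that agrees with the entry criterion: 10 and 12 g/dL, equivalently 100 and 120 g/L, if that was the intent. Keep the 30% decrease criterion as it is. Check which unit variable the PCSV program uses, since results are held in both systems, and do both before database lock. The cost is one table cell in the SAP and a check of one line of code.

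### The baseline gates in the hematocrit and (once its unit is corrected) hemoglobin PCSV rules leave larger falls from low baselines unflagged while smaller falls are flagged

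*SAP*

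**What the plan says.** SAP 11.3 gives two criteria for each of the two red-cell measures.

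- **Hematocrit:** a value of 0.32 v/v or less "and baseline >0.38 v/v", and a second criterion of a fall from baseline of 30% or more. The comment says "The first criteria is the follow up value". It does not say how the two criteria combine.
- **Hemoglobin:** a value of 10 or less with baseline above 12, both printed in g/L, and the same 30% fall. The comment says "Two criteria are independent", so either one flags. It adds "Criteria based upon decrease from baseline are more relevant than based on absolute value", lists optional fall categories of 30, 40 and 50 g/L, and ties the 30% figure to changes expected after surgery.

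Protocol 7.2.1 sets the entry floor at "Hemoglobin > 10 g/dL". It sets none for hematocrit. SAP 6.1 takes baseline as the last valid value before study drug; the scheduled Visit 2 hematology sample is pre-operative (SAP Table 4). SAP 5.8.3 reports the number and percentage of participants with treatment-emergent PCSVs, and descriptive statistics for results and change from baseline by visit.

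**The concern.** A baseline gate on a low-value flag is meant to stop values that were already low from counting as new. Here part of the eligible population lies at or below the gate. Those participants can be flagged only by a 30% fall, while participants just above the gate are flagged for falls of 16 to 20%. A larger loss ending at a lower value can then go uncounted while a smaller loss ending at a higher value is counted.

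The people affected start with the least reserve, in a trial whose main safety question is bleeding. The laboratory counts are also a useful cross-check, because treatment is open label and the adjudication committee classifies bleeding events that investigators record and send to it. A laboratory count does not depend on that step.

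**Working it through.** **Rule.** With baseline b and follow-up value f, flag if (f ≤ L and b > B) or (b − f)/b ≥ 0.30. For hematocrit, L = 0.32 and B = 0.38 (SAP 11.3). For hemoglobin, L = 10 and B = 12, in the unit under test. The hematocrit criteria are taken as independent; if both were required, fewer values would be flagged.

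**1. Hematocrit, as printed**

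| Change | Fall | Absolute rule | 30% rule | Flagged |
|---|---|---|---|---|
| 0.38 to 0.27 | 0.11/0.38 = 28.9% | no (baseline not above 0.38) | no | no |
| 0.39 to 0.32 | 0.07/0.39 = 17.9% | yes | no | yes |
| 0.40 to 0.32 | 0.08/0.40 = 20.0% | yes | no | yes |

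The inversion is present in the rule as written.

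**2. Hemoglobin, as printed in g/L.** Entry above 10 g/dL means above 100 g/L, so every eligible participant exceeds the 12 g/L gate and it excludes nobody. Reaching 10 g/L takes a fall of (101 − 10)/101 = 90.1% from the bottom of the range, or (150 − 10)/150 = 93.3% from 150 g/L. The 30% rule fires long before that, so the absolute rule adds nothing and there is no inversion. The row's own optional falls of 30 to 50 g/L could not occur from a baseline of 12 g/L, and the bleeding definition in SAP 4.5.2 uses a 20 g/L fall. The cut-offs were therefore almost certainly meant as 10 and 12 g/dL (100 and 120 g/L). That is an inference.

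**3. Hemoglobin, read in g/dL**

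| Change | Fall | Absolute rule | 30% rule | Flagged |
|---|---|---|---|---|
| 12.0 to 8.52 | 3.48/12.0 = 29.0% | no | no | no |
| 11.0 to 7.8 | 3.2/11.0 = 29.1% | no | no | no |
| 12.1 to 10.0 | 2.1/12.1 = 17.4% | yes | no | yes |
| 12.5 to 10.0 | 2.5/12.5 = 20.0% | yes | no | yes |

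Correcting the unit alone would therefore create in this row the inversion already present for hematocrit.

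**4. Test of the replacement rule.** Replace b > B with a decrease of at least B − L: 12 − 10 = 2 g/dL, and 0.38 − 0.32 = 0.06.

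- Above the gate nothing changes: b > 12 and f ≤ 10 already imply a fall of more than 2, and b > 0.38 with f ≤ 0.32 implies more than 0.06.
- The missed examples are caught: 11.0 to 7.8 falls 3.2 and ends below 10; 0.38 to 0.27 falls 0.11 and ends below 0.32.
- No larger absolute fall to a lower value can be unflagged while a smaller one to a higher value is flagged. If the smaller one is flagged by the absolute rule, the larger one also meets both parts of it. If it is flagged by the 30% rule, the larger one has a higher ratio, since fall/(fall + final value) rises with the fall and drops as the final value rises.

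**5. Size, on assumptions.** The documents give no distributions. Assumed: baseline hemoglobin mean 13.0 to 14.0 g/dL, SD 1.3, truncated above 10; one fall per participant, mean 2 to 3 g/dL, SD 1; 120 per arm.

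- Baseline of 12 or less: 6.1% to 21.2%, or 0.061 × 120 ≈ 7 to 0.212 × 120 ≈ 25 per arm.
- Flagged within that group: about 8% to 35% under the current rule (read in g/dL), 50% to 84% under the replacement.
- Missed per arm: about 25.4 × (0.842 − 0.346) = 12.6 at the high end and 7.3 × (0.50 − 0.077) = 3.1 at the low end.
- Above 12 g/dL, the two rules agreed for every simulated participant.
- Hematocrit, assumed mean 0.40 to 0.42 and SD 0.035: 13% to 28% have a baseline of 0.38 or less.

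**The case against.** **Baseline conditions are the table's convention.** Most of its laboratory rows have one, which suits a treatment-emergent count. That stands as an explanation. But for hemoglobin the entry floor lies below the intended gate, and the same table's systolic and diastolic pressure rows already use a threshold plus a decrease.

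**The 30% figure was chosen for the post-operative setting, and optional fall categories exist.** Both are true. The 30 g/L category would catch 11.0 to 7.8 (32 g/L). But these categories are permitted, not committed to; they start at 30 g/L; and none is given for hematocrit. The replacement rule will flag some expected surgical loss: under the assumptions above, half or more of the low-baseline group. That cost is real.

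**Any pair of thresholds produces anomalies.** Partly right. Under the replacement, 12.0 to 10.0 (16.7%) is flagged and 10.1 to 8.2 (1.9 g/dL, 18.8%) is not. This inversion is in percentage terms only and arises for falls just under 2 g/dL. A change from 14.0 to 10.1 stays unflagged under both rules, but it ends above 10 and so is not an inversion.

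**Stronger readings the documents do not support.** A reader might infer that the printed hemoglobin rule excludes anaemic participants. As printed in g/L it excludes nobody; the gap appears only after the unit is corrected. A reader might also infer that bleeding would be missed. Bleeding is adjudicated blind, without this gate, and hemoglobin changes and transfusions are recorded for each event (SAP 5.8.2). Nor is the major-bleeding fall a benchmark for a laboratory flag: "There should be an associated fall in hemoglobin level of at least 20 g/L (1.24 mmol/L" applies only alongside surgical-site bleeding that meets further conditions, and the extrasurgical criterion requires overt bleeding.

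**Conclusion.** The point holds and is minor. The hematocrit inversion is in the rule as printed. The hemoglobin row has a unit error that disables its absolute rule, and the same inversion follows once the unit is put right. Neither conclusion needs a distributional assumption, though the intended g/dL unit is inferred.

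The reach is limited to the PCSV counts in the descriptive laboratory tables. No endpoint, adjudicated bleeding result or decision depends on them, the same rule applies in all arms, and SAP 5.8.3 still reports change from baseline by visit. The 30% rule continues to catch the largest losses.

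The 3 to 13 participants per arm rest wholly on assumed baseline and fall distributions, and on counting misses against the replacement rule. They show a plausible order of size and are not an estimate from the plan.

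**What to change.** Amend two rows of SAP 11.3 before database lock:

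- **Hemoglobin:** correct the unit to g/dL (or print 100 g/L and 20 g/L). Absolute criterion: 10 g/dL or less and a decrease from baseline of at least 2 g/dL.
- **Hematocrit:** 0.32 or less and a decrease from baseline of at least 0.06. State that the two criteria are independent, as the hemoglobin row does.
- **Both:** keep the 30% criterion. State whether the optional hemoglobin fall categories will be used.

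No new data are needed, and SAP 6.3 already covers missing values for PCSVs that combine a change with a threshold. Every flag for a baseline above the intended gate is kept. The cost is more flags in all arms, some reflecting expected surgical loss; a table footnote saying so would be enough.
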